4.3. Randomization

This a single arm study and randomization is not applicable.

4.4. Clinical Assessments

Clinical and laboratory assessments were conducted at screening and on days 0, 14, 30, 60, 100 and 180. Patients received TCR $\alpha\beta$ T cell and CD19+ B cell depleted HSC on day 0. Unless otherwise protocol-specified, patients received the BPX-501 infusion on day 14+/- 4 days.

Clinical assessment, laboratory investigations, radiological investigations, and microbiological investigations will be conducted as per protocol schedule of assessments Table 1. Adverse events will be followed throughout the study period. In this study protocol, the scheduled study follow-up for each patient defined as 180 days. Further details of the schedule of assessments recorded on the electronic Case Report Form (eCRF) at each visit are provided in Table 1.

A full description of the study design, including inclusion/exclusion criteria, is provided in the study protocol.

5. PLANNED ANALYSES

5.1. Interim Analyses

Outside of safety monitoring, no formal interim analyses were planned for this study.

5.2. Final Analysis

The primary analysis will be conducted after the last patient enrolled has completed 180 days of follow-up and the source-verified data can be extracted from the clinical study database. A final analysis will be performed after the last subject under the UK version of the protocol has completed at least 2 years of follow-up.

6. STATISTICAL METHODS AND DATA HANDLING

6.1. Analysis Populations

The following analysis populations are defined for the study:

(i) *Enrolled Population (EP)* – Defined as all patients who signed informed consent, were assessed for inclusion/exclusion criteria during the screening period, and who were considered eligible for enrollment and post-enrollment follow-up. This population will be used to present overall study disposition data and for summarizing the total number of patients screened and considered eligible for the study.

(ii) *HSCT Safety Population (HSP)* – Defined as all patients in the enrolled population (EP) who received Hematopoietic Stem Cell Transplantation (HSCT). Only SAEs were reported in subjects prior to receiving BPX-501. The HSP therefore represents the analysis population for certain analyses of SAEs as well as disposition and outcomes in subjects who did not go on to receive BPX-501 for any reason.

(iii) *BPX-501 Safety Population (BSP)* – Defined as all patients who received HSCT and went on to receive any dose of BPX-501. Unless otherwise specified, this will be the default primary safety analysis population.

(iv) *Intent-to-treat Population (ITT)* – Given that this is a single-arm study, a “Full Analysis Set” (FAS) population is proposed to serve as the ITT population from which to provide estimates of treatment effects in subjects receiving BPX-501. The FAS/ITT population includes all patients treated with HSCT who received BPX-501 at the dose of 1×10^6 cells/kg.

(v) *Per Protocol Populations (PP)* – Defined as all patients in the ITT/FAS analysis population who were infused with BPX-501 at the dose of at least 1×10^6 cells/kg within a dosing around Day 14 (+/- 4 days) or Day 21 (+/- 14 days) after HSCT. The primary and key secondary efficacy analyses may be repeated on the PP populations as a means of characterizing the robustness of any outcome results.

(vi) *Rimiducid Population (RP)* – Defined as all patients who received at least one dose of rimiducid for the treatment of acute or chronic GvHD.

(vii) *Rimiducid Pharmacokinetics Population (RPK)* – Defined as all patients who received at least one dose of rimiducid for the treatment of acute or chronic GvHD and have a plasma sample to measure rimiducid concentrations over time.

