3.2. Study Endpoint(s)

Endpoints will be further defined in subsequent sections. Unless otherwise specified, time-to-event endpoints will be calculated from the date of HSC infusion. If a patient received more than one HSCT, the time of the last HSC infusion immediately preceding infusion with BPX-501 will be the transplant date.

Primary Endpoint:

Event-Free Survival (EFS) at 180 days. Events are defined as the first occurrence of either transplant-related mortality (TRM) for non-malignant patients or non-relapse mortality (NRM) for malignant patients, severe GvHD (Grade 2-4 acute organ GvHD or extensive/moderate-severe chronic GVHD), and life-threatening infections (Grade 4).

NB: In the BPX-501 protocols, the terminology 'extensive' chronic GvHD was used. For the purposes of the primary analysis and for the rest of this SAP, extensive chronic GvHD will be defined as moderate or severe chronic GvHD. 'Overall' chronic GvHD or chronic GvHD without a qualifier will be interpreted as mild, moderate or severe chronic GvHD.

The following secondary endpoints are in the BP-004 protocols, although additional endpoints and analyses are described below in subsequent sections of this document.

Secondary Endpoints:

- (i) Transplant-Related Mortality (TRM) in patients with non-malignant diagnoses or Non-Relapse Mortality (NRM) in patients with malignant diagnoses at 100 and 180 days
- (ii) Cumulative incidence and severity of acute GvHD (any Grade 2-4 or Grade 3-4) as well as overall and moderate-severe chronic GvHD at 180 days.
- (iii) Time to resolution of acute GvHD after administration of rimiducid
- (iv) Immune reconstitution as determined by T cell subsets up through 180 days
 - a. Absolute CD3 count
 - b. Absolute CD4 count

- c. Absolute CD8 count
- (v) Time-to-immune reconstitution defined by CD3 count > 500 cells/uL; CD4 count > 200 cells/uL; CD8 count of 200 cells/uL
- (vi) Disease-Free/chronic GvHD Survival (DFGS) defined as the first of either disease recurrence, death from any cause, or chronic GVHD
- (vii) Disease status within the following disease indications at 180 days:
 - a. Primary immune disorders as determined by CD3 T cell count ≥ 500 cells/uL and normal levels of IgA and IgM
 - b. Haemoglobinopathies as determined by incidence of RBC transfusion independence for 8 consecutive weeks and untransfused haemoglobin of ≥ 8.5 g/dL

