6.2.3. Baseline Definition

For this study, the patient begins study treatment on the day of hematopoietic stem cell transplantation (HSCT) defined as Day 0 in the protocol and study Day 1 for analysis. It is noted that the study schedule from the protocol refers to the reference date as Day 0. For reporting purposes, CDISC standards will be used, referring to the first day as Day 1.

If a patient received multiple HSCTs, the date of HSCT which occurred immediately before administration of BPX-501 will be considered study Day 1.

For all endpoints requiring a baseline reference, e.g., comparison with a post-baseline value, the baseline value will be the last non-missing result prior to HSCT.

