6.4. Efficacy Analysis

The analysis of primary and secondary endpoints will be based on the ITT (FAS) population as the primary analysis population. Any supportive sensitivity analyses may be assessed on the PP population or other subgroup defined below. Final decisions on different exploratory subgroups will be determined prior to the time of primary analysis.

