6.4.1. Primary Efficacy Analysis

The primary efficacy endpoint is Event-Free Survival (EFS) up to 180 days using the ITT (FAS) population. Events corresponding to EFS outcome include

- Transplant-Related Mortality (TRM) for non-malignant patients or Non-Relapse Mortality (NRM) for malignant patients, defined as the time from transplant until death without evidence of recurrence or relapse,
- Severe GvHD, defined as any case of grade 3-4 acute GvHD regardless of organ involvement, any case of grade 2 acute GvHD with visceral (non-skin-only) organ involvement, or any case of moderate-severe chronic GvHD, and
- Life-threatening infections (Grade 4).

For patients with multiple events, the event that occurs first and the corresponding time will be used for the EFS. Subsequent EFS-qualifying events will be provided in a listing in order to describe longer-term outcomes observed in patients with a primary EFS event. Patients who do not experience an EFS-qualifying event will be censored on the last day of observation. EFS will be calculated from the date of HSCT transplant defined above.

Kaplan-Meier techniques will be used to estimate EFS at day 180. When estimable, additional summary statistics will include the median, minimum, maximum, the 25th and 75th percentiles of EFS along with the number of events and censored observations. Kaplan-Meier plots with descriptive summary statistics will be presented along with the number of patients at risk at various time points.

An additional sensitivity analysis of EFS may be performed using an expanded definition of EFS-qualifying events to include patients with skin-only grade 2 acute GvHD.

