6.7. Additional Exploratory Analyses

Other exploratory subgroup analyses to characterize safety and efficacy activities for BPX-501 may be conducted. These additional exploratory analyses will be decided at the time of final data analysis.

Sparse PK sampling collected from patients that receive rimiducid will be used to determine the concentration time profile of rimiducid in plasma and summarized as described above. Rimiducid plasma concentration data collected from these subjects will be used as part of a population PK modeling and meta-analysis that will be presented in a separate document. Additional PK assessments may be performed as deemed appropriate.

In addition to the pharmacodynamic and translational analyses specified above, further exploratory analyses are planned and will also be presented in separate documents. These analyses include, among others, analysis of CD45RO/CD45RA/CD62L/CCR7, T cell diversity, and thymic function.

The following additional efficacy analyses were not specified in the protocol, but are being proposed in order to assess longer-term outcomes beyond 180 days and to harmonize with other

study protocols investigating the use of BPX-501. The analyses will be conducted in the ITT population, and, possibly, in the PP population as well.

- (i) Transplant-Related Mortality and Non-Relapse Mortality, defined earlier, at 1 year and 2 years from the time of HSCT. TRM and NRM at those time points will be estimated using a Nelson-Aalen cumulative incidence function.
- (ii) Overall Survival, defined as the time from HSCT to death due to any cause, at 180 days, 1 year and 2 years. Overall survival will be analyzed in all patients as well as stratified by disease subtype (malignant and non-malignant). Overall survival at those time points will be estimated using a Kaplan-Meier survival function.
- (iii) Disease-Free Survival, defined as the time from HSCT to disease recurrence or death, whichever occurs first, in subjects with non-malignant disease. DFS will be estimated at 180 days, 1 year and 2 years using a Kaplan-Meier survival function.
- (iv) Relapse-Free Survival, defined as the time from HSCT to disease relapse or death, whichever occurs first, in subjects with malignant disease. RFS will be estimated at 180 days, 1 year and 2 years using a Kaplan-Meier survival function.

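### Survival and transplant mortality are timed from HSCT but estimated only in patients later infused with BPX-501, with no supportive estimate in all transplanted patients

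*SAP*

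**What the plan says.** The SAP is written for BP-004 and also covers outcomes after Day 180 that draw on BP-404.

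**Clock.** Section 3.2 sets the general rule: "Unless otherwise specified, time-to-event endpoints will be calculated from the date of HSC infusion". Section 6.4.1 applies it to the primary endpoint: "EFS will be calculated from the date of HSCT transplant defined above". The same section times TRM/NRM from transplant. Section 6.7 starts OS, DFS and RFS at the same point, for example "Overall Survival, defined as the time from HSCT to death due to any cause, at 180 days, 1 year and 2 years".

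**Population.** Section 6.4 states: "The analysis of primary and secondary endpoints will be based on the ITT (FAS) population as the primary analysis population". For the longer-term outcomes section 6.7 states: "The analyses will be conducted in the ITT population, and, possibly, in the PP population as well". Section 6.1 defines that set: "The FAS/ITT population includes all patients treated with HSCT who received BPX-501 at the dose of" 1×10^6 cells/kg. The per-protocol set is drawn from within it.

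**Gap between the two.** Section 4.1 places BPX-501 at 14 ± 4 days after the graft, or 21 ± 14 days under some protocol versions.

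**Uninfused patients.** Section 6.1 defines an HSCT Safety Population (HSP) for certain SAE analyses and for the disposition and outcomes of patients who never received BPX-501. Sections 6.3.1 and 6.5 and listings 16.2.3.2, 16.2.3.4 and 16.2.7.2.2 add counts, reasons for exclusion and individual data.

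**The concern.** A patient enters the analysis set by surviving to, and receiving, an infusion that happens after time zero. The days between HSCT and infusion are therefore death-free by construction, yet they count as time at risk. The SAP describes no delayed entry, landmark or infusion-based clock.

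For OS and TRM/NRM the guarantee is strict. For EFS it is partial, because a qualifying non-fatal event before infusion can still count if the patient is later infused.

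Results labelled ITT and timed from HSCT will be read as outcome from transplant for everyone transplanted. If some patients died before infusion, or were not infused because they were doing badly, survival is too high and TRM/NRM too low for that reading. TRM/NRM is the most sensitive in relative terms, since early deaths can be a large share of it. Loss unrelated to prognosis causes no bias.

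**Working it through.** **The plan's own figures.** Section 4.2 gives power of about 91% (100 MUD, 160 BPX-501) and 84% (70 and 140), with EFS of 88% and 91% and a 10-point margin. That paragraph states no alpha; I used one-sided 0.025, from the two-sided 5% in section 6.2.1. With a pooled null variance, power = Φ[(0.13 − 1.96·SE0)/SE1].
- 100/160: SE0 = 0.0385, SE1 = 0.0396, power 91.6%.
- 70/140: SE0 = 0.0439, SE1 = 0.0458, power 83.2% (85.0% with the Farrington-Manning variance).

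The stated powers reproduce. Below I use only the 91% EFS assumption, which should not be confused with the 91% power.

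**Step 1: guaranteed death-free time.** From section 4.1:

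| Infusion window | Share of 100 days | Share of 180 days |
|---|---|---|
| Day 10 to 18 | 10% to 18% | 5.6% to 10.0% |
| Day 7 to 35 | 7% to 35% | 3.9% to 19.4% |

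**Step 2: is there a planned estimate that includes the uninfused?** The per-protocol set is a subset of the ITT/FAS. The EFS sensitivity tables 14.2.1.2 to 14.2.1.5 (acute GvHD definition, dosing window, death from any cause, dose) are not described as adding uninfused patients. No Kaplan-Meier or cumulative incidence analysis is specified for the HSP.

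**Step 3: EFS at Day 180.** Let f be the share of transplanted patients never infused and g the share of those with an EFS event by Day 180. Neither is in the documents, so both are assumptions. EFS in infused patients is set at the SAP's 0.91.

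EFS(all transplanted) = 0.91(1 − f) + f(1 − g), so the overstatement is f(g − 0.09).

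| f | g = 9% | g = 50% | g = 100% |
|---|---|---|---|
| 1% | 91.0% (0) | 90.6% (0.41) | 90.1% (0.91) |
| 3% | 91.0% (0) | 89.8% (1.23) | 88.3% (2.73) |
| 5% | 91.0% (0) | 89.0% (2.05) | 86.5% (4.55) |

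Brackets give the overstatement in percentage points.

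**Step 4: scale.** The 95% half-width at 91% with n = 160 is 1.96·√(0.91·0.09/160) = 0.044, or 4.4 points. The bias is well inside this at f = 1% and about equal to it at f = 5% with g = 100%.

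**Step 5: TRM/NRM.** Let T be the true value in all transplanted patients and d the share who die before infusion, with everyone else infused. The FAS value is (T − d)/(1 − d). With assumed T = 5% and d = 1%: 0.04/0.99 = 4.04%. The reported figure is lower by 0.96 points, about a fifth of the true value (0.96/5 = 19%).

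**The case against.** The strongest reply is that the conditioning is declared. Section 6.1 says the FAS is there to estimate effects in patients receiving BPX-501, and it gives the uninfused their own population. That stands for the choice of population. It does not justify starting that population's clock at a date before membership is decided.

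Several stronger readings are tempting, but the documents do not support them:

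- *Uninfused patients are hidden.* They are not. Section 6.3.1, table 14.1.1.1 and the listings named above will largely show how many were not infused and why. Table 14.3.2.8 may also count their deaths, though its population is not stated. Only a rate or curve is missing.
- *The non-inferiority comparison with MUD transplant loses power or error control.* The entry rules of the MUD cohort are not in these documents, and section 6.4 specifies no non-inferiority test. No such claim can be made.
- *Pre-infusion EFS events in infused patients are missed because only SAEs were collected before BPX-501.* The SAP states this limit openly. A life-threatening infection would meet the SAE definition in Protocol 9.1.3, and Protocol Table 3 asks for all GvHD whatever its onset. That is BP-404 text, so it does not settle BP-004 practice, but the inference is thin.
- *The transplant date is chosen to drop early events.* Section 6.2.3 says that, with several grafts, "the date of HSCT which occurred immediately before administration of BPX-501 will be considered study Day 1". No passage describes a second on-study graft before infusion, and section 6.3.3 treats prior HSCT as a baseline characteristic.
- *One- and two-year survival is inflated because BP-404 admits only patients beyond Day 180.* SAP section 2 allows these analyses to pool BP-004 and BP-404 data, and section 6.7 runs them in the ITT population. The inflation would not apply to that pooled analysis.

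It is also fair to say that the size is wholly assumed.

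**Conclusion.** The mismatch between clock and population is plain in the text, and confidence in the mechanism is high. Its direction is conditional: it flatters survival and TRM/NRM only if uninfused patients did worse than infused ones.

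The size cannot be derived. Under the stated assumptions (1% to 5% never infused, and 91% EFS in the infused), Day-180 EFS is overstated by 0.4 to 2.1 points if half of the uninfused fail, by 0.9 to 4.6 points if all fail, and by nothing if they match the infused. A true TRM/NRM of 5% would appear as 4.0% if 1% die before infusion.

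The FAS is a legitimate primary set. What is missing is a supportive estimate and an accurate label. This should be fixed because it costs little, not because the FAS results are shown to be wrong.

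**What to change.** 1. **SAP 6.4 and 6.7.** Keep the FAS primary. Add supportive OS and TRM/NRM from HSCT in the HSP, to Day 100 and Day 180 only, with EFS where pre-infusion SAE data allow. Do not go beyond Day 180: uninfused patients cannot enter BP-404 (Protocol 5.4 and 5.5), and the documents do not state how long they are followed.
2. **Dose.** Do not restrict this analysis to phase II. Protocol 7.2 shows that 1×10^6 cells/kg was also a phase I level, and the FAS has no phase limit, so such a restriction would drop FAS members. If a dose restriction is wanted, define it by the BPX-501 dose level planned at enrolment, which keeps FAS patients from both phases.
3. **Time zero.** For this analysis, use a date that does not depend on receiving BPX-501, such as the first on-study HSCT. The rule in section 3.2 ("the time of the last HSC infusion immediately preceding infusion with BPX-501 will be the transplant date") cannot be applied to a patient who was never infused.
4. **Labels.** Describe every FAS estimate timed from HSCT as conditional on surviving to, and receiving, BPX-501.

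The cost is one supportive analysis from death and SAE data on the HSP, one sentence on time zero, and table labels. Estimates may be slightly less favourable, and the pre-infusion part of EFS would rest on SAEs alone.

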6.2. Statistical and Analytical Methods

6.2.1. General Statistical Approach Summaries

Data will be summarized with respect to each of the performance outcomes assessed, pooled across all the investigative sites and, in many cases, stratified by type of disorder (malignant or non-malignant). Continuous endpoints will be summarized using the number of observations, mean, median, standard deviation or interquartile range, and minimum and maximum values. Categorical endpoints will be summarized using the number of observations and percentages. Time-to-event assessments will be summarized using either Kaplan-Meier or Nelson-Aalen statistical techniques, as appropriate, with display of parameter estimates at pre-defined timepoints along with the number of censored observations. Unless otherwise stated, confidence intervals will be constructed at the 95% confidence level. Any potential statistical tests will be two-sided, with type 1 error rate of 5%. *P*-values will be rounded to three decimal places, with *p*-values less than 0.001 will be reported as <0.001, and *p*-values greater than 0.999 will be reported as >0.999.

Data listings will be sorted by treatment, dose, site identification number, subject identification number and visit.

The primary analysis is planned to be conducted after the last patient enrolled has either completed 180 days of follow-up on study or withdraws from the study prior to 180 days. Unless otherwise stated, statistical analysis will be performed using SAS statistical software (Version 9.4, unless otherwise noted). Adverse events were coded using MedDRA version 18.0. Concomitant medications were coded using World Health Organization (WHO) coding standards and the WHO 2015 drug dictionary. For key adverse events and concomitant medications, any coding changes between the versions used for analyses and more recent versions will be highlighted.

For rimiducid plasma concentration data, summary statistics will include the arithmetic mean, arithmetic standard deviation, median, minimum, maximum, and number of observations. Data listings will be provided for all subjects up to the point last evaluable sample collection. Any subjects excluded from the relevant population will be highlighted. For the calculation of summary statistics and statistical analysis, unrounded data will be used.

6.2.2. Missing Data and Handling of Dropouts

Unless otherwise specified, missing data will not be imputed for efficacy variables. For subjects who withdrew from the study prior to study completion, all data attained up to the point of discontinuation will be listed and included in data summaries. Patients will be censored at the time of their last documented study visit prior to or at the time of study withdrawal.

The term missing date refers to a completely missing date or to a partial date where month, day or year are missing. Unless otherwise stated, the handling of partial missingness of dates will impute using midpoint values. That is, missing days will be imputed as the 15th of the month and

missing months will be imputed as July 1st, unless a more suitable value can be imputed based on study or treatment start and end dates.

If an adverse event (AE) resolution date is completely missing, the duration (ongoing/resolved status) will be checked before imputing a date, noting when the AE started in relation to study treatments. If the ongoing flag is missing, then it is assumed that the AE is still present (i.e., do not impute a date).

Adverse event relationship missing: If the relationship for an adverse event is not recorded, it will be reported as missing in the presentation of listings and summaries of incidence results. Assessments of relatedness to AP1903/rimiducid should only apply for AEs which occur on or after the date of first rimiducid dose.

Adverse event severity missing: If the severity of an adverse event is missing, the severity will be assumed to be missing when summarizing data. Missing information will be reported as missing in the subject listings.

Non-study medication (concomitant medications, steroids) start and stop dates missing: If the start and/or stop dates of non-study medication use are incomplete or missing, the use will be assumed to be concomitant, unless the incomplete date information clearly indicates that the use stopped prior to the on-study-date. Missing or incomplete information will be reported as missing/incomplete in the subject listings.

For pharmacology and pharmacokinetic data, the following rules will be applied if there are values that are below the limit of quantitation (BLQ) or if there are missing values (e.g., no result [NR]) in a plasma concentration data series to be summarized.

- For the calculation of summary statistics, BLQ values will be set to zero.
- If an embedded BLQ value is considered anomalous within the concentration-time profile, this value will be excluded from the summary statistics.
- Where there is NR, these will be set to missing.
 - If there are less than three values in the data series, only the min, max, and N will be presented. The other summary statistics will be denoted as not calculated (NC). BLQ is considered a value.
 - If all the values are BLQ, then the arithmetic mean, arithmetic SD, median, min, and max will be presented as zero.
 - If the value of the arithmetic mean or median is below the assay LLOQ, it will be presented as zero.

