#### **5.4 Subject Inclusion Criteria**

1. Signed written informed consent by the patient or the patient's guardian for children who are minors.

2. Enrolled on BP-004 protocol, received BPX-501 infusion, completed or discontinued from the study, and are beyond Day +180.

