## 7.2 Trial Design

The BP-004 Phase I trial design consisted of 3 different escalating doses ( $2.5 \times 10^5$ ,  $5 \times 10^5$ ,  $1 \times 10^6$  cells/kg recipient total body weight) in all patient populations and further escalation of 2 doses ( $2 \times 10^6$ ,  $4 \times 10^6$  cells/kg recipient total body weight) were evaluated in patients with malignant disease only.

Patients were enrolled at the recommended dose for a maximum of 175 pediatric patients total (for both phases), and the minimum active study follow-up for each patient was 180 days in protocol BP-004.

Patients enrolled on the BP-004 study who received BPX-501 T-cells and are beyond Day 180 will be requested to enroll on this long-term follow up protocol, regardless of whether they completed or discontinued from the parent study BP-004.

The follow-up time for evaluation for overall survival and disease-free survival in patients with malignant disease and patients with non-malignant disease will be 1 and 2-years post-transplant. Relapse-free survival in malignant patients will be evaluated at 1 and 2 years. Long term follow-up for survival and gene therapy safety will be 15 years after BPX-501 treatment.

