This Statistical Analysis Plan (SAP) is based on the BP-004 study protocol and is intended to provide the statistical methods and summaries for the analysis of the data arising from the clinical trial (Protocol BP-004, Italy Version 10.0, 2 April 2018; United Kingdom Version 7.0,c 2 April 2018). Once completing the initial 180-day follow-up period, subjects enrolled into the Italian version of the BP-004 protocol were enrolled into a follow-up protocol, BP-404. Analyses presenting data beyond Day 180 in this SAP may therefore pull data from all three protocol sources (Italy and United Kingdom BP-004; Italy BP-404). The analysis approaches and methods outlined in this document, if different from the respective protocols, will supersede those specified in the protocol.

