4. STUDY DESIGN

This phase II study is a multi-center single-arm extension study following completion of a phase I dose escalation study, where subjects were treated in a 3+3 dose escalation design.

As stated in the protocol, this study enrolled any infant (1 month-24 months), child (2-11 years) or teenager (12-18 years) with malignant hematological disorders in complete morphological remission or non-malignant hematological disorders eligible for an allogeneic transplantation and lacking either a related or unrelated HLA-matched donor or whose disease status does not allow the extensive wait for an unrelated donor. Patients will have access to a partially matched family donor who will provide PBMCs for creating the BPX-501 modified T cells as well as the HSCT.

Up to 175 pediatric patients were to be enrolled in this phase II extension trial at the dose of 1×10^6 cells/kg regardless of disease classification (malignant or non-malignant). The study follow-up for each patient will be at least 180 days.

After completing the study, eligible subjects will be enrolled in a gene therapy follow-up study for a total of 15 years. Given the various protocols referenced in this document, additional follow-up beyond 180 days is within scope of this SAP and longer-term results may be presented for supportive purposes.

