6.3.1. Subject Disposition

Subject disposition will be presented for the appropriate analysis populations defined above. The following categories will be displayed in descriptive statistics summary tables:

- Subjects enrolled
- Subjects in the HSCT Safety Population (HSP)
- Subjects in the BPX-501 Safety Population (BSP)
- Subjects in the ITT (FAS) Population
- Subjects completed study (180-day follow-up)
- Subjects discontinued from the study early and reason of discontinuation.

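### SAP 6.2.2 read literally censors BP-004 discontinuers before Day 180 for OS, DFS and RFS, even when BP-404 later records their 1- and 2-year outcome

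*SAP*

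**What the plan says.** SAP 6.2.2 sets one general rule for dropouts. It keeps, "For subjects who withdrew from the study prior to study completion, all data attained up to the point of discontinuation", and then adds: "Patients will be censored at the time of their last documented study visit prior to or at the time of study withdrawal". It does not say which study's withdrawal is meant.

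SAP 6.7 (items ii to iv) gives OS, DFS and RFS a time origin, an event and a Kaplan-Meier estimate at 180 days, 1 year and 2 years, but no censoring rule. Two other endpoints do have one: EFS (SAP 6.4.1) is censored on the final day of observation, and disease-free/chronic-GvHD-free survival (SAP 6.4.2 vi) at the last visit on record.

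The SAP ties study completion to Day 180. The disposition table in 6.3.1 has the line "Subjects completed study (180-day follow-up"), and 6.2.1 times the primary analysis by when the last patient has "completed 180 days of follow-up on study or withdraws from the study prior to 180 days".

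BP-404 takes in both groups. Protocol 5.4 admits BPX-501 recipients who "completed or discontinued from the study, and are beyond Day +180", and Protocol 7.2 asks them to enrol "regardless of whether they completed or discontinued from the parent study BP-004". The SAP describes entry for completers only: "Once completing the initial 180-day follow-up period, subjects enrolled into the Italian version of the BP-004 protocol were enrolled into a follow-up protocol" (Section 2) and "After completing the study, eligible subjects will be enrolled in a gene therapy follow-up study" (Section 4).

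**The concern.** OS, DFS and RFS at 1 and 2 years are the primary endpoints of BP-404 (Protocol synopsis and 5.1). A patient who discontinued BP-004, say, on Day 100 and then enrolled in BP-404 will have the outcome that these endpoints need. Under SAP 6.2.2 as written, that patient's OS time stops at or before Day 100, and nothing in SAP 6.7 restarts it.

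Two things are at stake. Information already collected is lost. The estimates are also biased if leaving BP-004 is linked to prognosis: too high if leavers do worse, too low if they do better. Such a bias does not shrink with sample size and does not show in the confidence interval. In addition, two programmers following this SAP could derive different OS dates for the same patient.

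**Working it through.** **Text.** The conclusion needs four links.

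1. SAP 6.7 is silent on censoring, so the general rule in 6.2.2 applies by default.
2. Because completion means 180 days, withdrawal in 6.2.2 most naturally means leaving BP-004 before Day 180.
3. Protocol 5.4 and 7.2 let such patients into BP-404.
4. SAP Section 2 says that analyses beyond Day 180 may draw on BP-404, but it describes entry only for patients who completed 180 days and sets no censoring date. It also says that the SAP prevails over the protocols where they differ.

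**Size.** The plan states no figure to reproduce. The only input taken from the documents is N = 160 (SAP 4.2). The rest is assumed: exponential survival with 2-year OS of 77% in patients who stay; 10% assigned to discontinue BP-004, uniformly over days 14 to 180; later hazard k times that of patients who stay; 70% of discontinuers alive at Day 180 enter BP-404 then.

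Daily hazard: λ = −ln(0.77)/730 = 0.2614/730 = 0.000358.

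Literal rule: discontinuers leave the risk set while their hazard still equals everyone else's. Kaplan-Meier at day 730 therefore tends to exp(−730λ) = 77.0%, whatever k is.

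True 2-year OS = 0.9 × 0.770 + 0.1 × exp{−λW − kλ(730 − W)}, averaged over the discontinuation day W. At the midpoint, W = (14 + 180)/2 = 97, λ × 97 = 0.0347 and λ × 633 = 0.2266:

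- k = 0.5: exp(−0.0347 − 0.1133) = 0.862; true OS 77.9%; bias −0.9
- k = 2: exp(−0.0347 − 0.4533) = 0.614; true OS 75.4%; bias +1.6
- k = 3: exp(−0.0347 − 0.6799) = 0.489; true OS 74.2%; bias +2.8

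Simulation with 1,000,000 patients per scenario agrees. It also gives the bias when BP-404 follow-up is used with delayed entry. The difference between the two is the part caused by dropping BP-404 data:

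| Later hazard | Literal rule | Delayed entry | Due to dropping BP-404 data |
|---|---|---|---|
| ×0.5 | −0.90 | −0.33 | −0.57 |
| ×1 | +0.01 | 0.00 | +0.01 |
| ×2 | +1.57 | +0.60 | +0.97 |
| ×3 | +2.77 | +1.07 | +1.70 |

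(Percentage points of 2-year OS.)

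**Range.**

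- With 5% discontinuing, the literal-rule biases are −0.5, 0.0, +0.8 and +1.4, about half. The share due to BP-404 data halves too, to roughly 0.5 and 0.85 points at ×2 and ×3.
- If 30% or 90% re-enter, delayed entry at ×3 leaves +2.1 or +0.6, so the share is about 2.8 − 2.1 = 0.7 or 2.8 − 0.6 = 2.2 points.
- Censoring at the last scheduled BP-004 visit (SAP 4.4) instead of the withdrawal day moves the literal figures by about −0.1.
- A harsher setting: 15% discontinue at Day 120, when 95% are event-free; all are followed in BP-404; their later event risk is 50% against 15%. The overstatement is 0.95 × 0.15 × (0.50 − 0.15) = 5.0 points.

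**Precision** at equal hazards and N = 160: standard error 3.49 points under the literal rule and 3.33 with full vital status. The half-widths are 1.96 × 3.49 = 6.8 and 1.96 × 3.33 = 6.5.

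**Why delayed entry.** Adding the entrants as if observed continuously from transplant credits them with time during which they could not have been seen to die. At equal hazards this gives +0.16 points, or +0.3 if enrolment is spread over days 180 to 365. Delayed entry gives 0.0 in both cases.

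**The case against.** The strongest reply is that the literal reading goes against the SAP's own purpose. Section 2 lets data beyond Day 180 come from BP-404, Section 4 puts that follow-up in scope, and 6.7 proposes these analyses in order to look past Day 180. In a pooled analysis a BP-404 visit could count as a documented study visit. This makes it likely that the sponsor means to use the data. It does not settle the matter for discontinuers, because the wording is permissive and names completers only.

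A second reply is that 6.2.2 may only date patients with no known event. That does not help. An event-free discontinuer would still lose BP-404 follow-up, while deaths found later would count. With 10% withdrawn over 2 years, counting all later deaths without updating survivors biases OS by −1.0 point at equal hazards.

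Third, the stakes are limited. The SAP treats these as additional exploratory estimates without a test, and its own primary endpoint, EFS, has its own rule. This stands and limits the severity.

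A reader might infer more than the documents support:

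- That the rule costs +1.6 or +2.8 points at ×2 or ×3. Those figures compare with complete vital status. They include discontinuers who die before Day 180 or never enter BP-404, for whom BP-404 holds no data.
- That BP-004 completers also lose follow-up. They are not withdrawn in the SAP's sense. For a completer who later leaves BP-404, 6.2.2 may not apply at all.
- That every withdrawn patient must be traced. Protocol 6.1 promises monitoring after BP-404 withdrawal only where possible, and the BP-004 protocols are not among the documents.

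**Conclusion.** The point holds as a minor to moderate defect, confined to patients who discontinued BP-004 and then entered BP-404. The written rule censors them before Day 180 for outcomes that BP-404 exists to measure, and no other SAP text overrides it.

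On the main assumptions (10% discontinuing, 70% of those alive at Day 180 re-entering), the loss of BP-404 data moves 2-year OS by about +1.0 or +1.7 points at two or three times the hazard, −0.6 at half the hazard, and nothing at equal hazards. With 5% discontinuing it is about half as much. All of this lies inside a half-width of 6.5 to 6.8 points. The direction and size rest on assumed rates. The number of patients affected is not given and could be very small.

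**What to change.** Add to SAP 6.7:

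> Withdrawal from BP-004 is not a censoring event for OS, DFS or RFS in patients who enter BP-404. Their BP-404 follow-up is included, with delayed entry at BP-404 enrolment, because entrants are survivors beyond Day 180 by selection. OS is censored at the date last known alive, and DFS and RFS at the last disease assessment, across BP-004 and BP-404. For other withdrawn patients, post-withdrawal events count only where survivors and deaths are followed alike; otherwise these patients stay censored at withdrawal.

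Keep the 6.2.2 rule as a sensitivity analysis and report how many BP-004 discontinuers entered BP-404.

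Cost: a paragraph of SAP text, a derived last-known-alive date, and programming for entry times. No new visits and no additional tracing are needed. Downside: a small bias remains from discontinuers who never enter BP-404 (about +0.6 or +1.1 points at ×2 or ×3 in the main illustration).
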